Autoimmune encephalitis (AE) is a group of disorders caused by an immune-mediated disruption of brain function characterized by seizures, cognitive impairment, movement disorders and behavioral changes. These disorders have been increasingly recognized over the past 10 years as a treatable cause of rapidly progressive dementia, intractable seizures or psychosis. The best characterized forms of AE are associated with autoantibodies targeting cell surface or synaptic proteins. The most common encephalitis autoantibodies are specific for the N-methyl-D-aspartate receptor (NMDAR), leucine rich, glioma-inactivated 1 protein (LGI1) and contactin associated protein-like 2 (Caspr2). However, as of 2017, over a dozen other autoantibodies have been associated with AE and some patients with treatable AE have no recognized antibody marker.^{1, 2}

AE affects patients across all age groups, with some forms of the disease preferentially affecting pediatric patients. Increasing awareness and clinical experience indicates that AE is not rare as previously thought. At UT Southwestern Medical Center, for example, we retrospectively identified 64

Form A

IRB #	STU 2018-0185
26776	

AE cases over a 6 year period (2010-2015), and this is certainly an underestimation since awareness and clinical laboratory diagnostic tests have improved significantly in the past 4 years.

References

b. Current practice

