Subjects completing Phase 1 must be re-screened to subsequently participate in Phase 2 of this study. Phase 2 of the study is the double-blind placebo-controlled trial for which we are requesting funding support through Genentech.

Patients who meet the inclusion/exclusion criteria (Table 3) will be eligible to participate in the randomized double-blind placebo-controlled treatment trial. Subjects who meet the eligibility criteria for the treatment trial can participate even if they were not enrolled in Phase 1 of this study. Patients will be consented separately for the treatment trial.

Table 3: Inclusion/Exclusion criteria (Treatment Trial)**Inclusion criteria**

1. Age 18 or greater
2. Able to obtain informed consent from patient or appropriate designee
3. Possible autoimmune encephalitis as defined by Table 1
4. Completed initial treatment with iv steroids (at least 3000mg solumedrol) and plasma exchange (at least 3 exchanges) within the past 4 weeks

Form A

IRB #	STU 2018-0185
26776	

5. Presence of one (or more) of the following autoantibodies in serum or CSF

- NMDA receptor
- LGI1
- CASPR2
- DPPX

Exclusion criteria

1. Prior immunosuppression treatment in past year (other than steroids and plasma exchange)
2. Treatment with intravenous immunoglobulin in past year
3. Active malignancy requiring chemotherapy
4. Pregnancy
5. Evidence of active hepatitis or tuberculosis infection
6. Medical condition that (in investigators opinion) precludes the use of ocrelizumab

Patients in Phase 2 (treatment trial) will be evaluated with neuropsychological functional measures at baseline and during treatment (every 3 months). The complete battery of tests listed in Table 4 can be completed in about 40 minutes. The Texas Functional Living Scale (TFLS) and self-reported ADL score are part of the clinical outcome assessment.

Table 4: Neuropsychological testing battery

Test	Rationale
Texas Functional Living Scale (TFLS)	Objective measure of functional ability/instrumental ADLs
Lawton & Brody Instrumental Activities of Daily Living (IADL) Rating Scale	Self-report measure of instrumental IADLs Patient and informant administrations
Symbol-digit Modalities Test (SDMT)	Written and /or oral processing speed
Trail Making Test Parts A & B (TMT)	Visuomotor processing speed (TMTA) and set shifting/divided attention (TMTB)
Controlled Oral Word Association Test (FAS)	Phonemic verbal fluency
Hopkins Verbal Learning Test-Revised (HVLT-R)	Episodic verbal memory

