We also anticipate that ocrelizumab-treated subjects will show higher functional scores.

The criteria for the primary endpoint, treatment failure, is described in Table 5. At each clinical study visit, subjects will complete the global impression and IADL questionnaire, and the full panel of assessment tests will be performed every 3 months. Between study visits, the study coordinator will contact the subject every 2 weeks by telephone to inquire about adverse events and clinical status. If a subject or caregiver reports clinical worsening, the subject will complete the IADL questionnaire. Subjects with concern for clinical worsening will be brought in for unscheduled clinical assessment and completion of the TFLS.

Subjects who meet criteria for treatment failure will complete the final study visit procedures (12 month visit). At the investigators' discretion, subjects with early treatment failure during the first 6 months will be offered open label treatment with ocrelizumab (one dose of 600mg) or may proceed with best available alternative treatment in consultation with their primary doctors.

Form A

IRB #	STU 2018-0185
26776	

Estimated number of subject

We expect to identify up to 60 patients eligible for the phase 1 biomarker study, and we plan to enroll 22 patients in the double-blind treatment study (phase 2). Based on our previous retrospective studies, we anticipate that we can achieve this enrollment in 12-18 months.

Based on our own experience and case reports related to rituximab, we will be expecting a large effect size. Assuming a relapse rate of 15-20% in the ocrelizumab group and an 75-80% relapse rate in the placebo group, a sample size of 22 achieves 80% power to detect an effect size (W) of 0.6 (20% vs 80%) using a 1 degree of freedom Chi-Square Test with a significance level (alpha) of 0.05. This sample size would have a 73% power to detect an effect size of 0.55 and 65% power to detect an effect size of 0.5.

With 22 subjects, the Chi Square for this effect size would be significant ($p=0.03$) even for an effect size of 46% (e.g. 3 treatment failures out of 11 in the ocrelizumab group and 8 treatment failures in placebo group).

Setting for each phase:

For phase 1, subjects may be initially enrolled during hospitalization at Zale Lipshy Hospital or Clements University Hospital. Patients identified in the neurology clinics of the investigators may also be identified.

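### Does the 12-18 month forecast for 22 Phase 2 subjects conflict with the centre's own count of 64 cases in six years?

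*Combined protocol and SAP*

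**What the plan says.** Section 4.a, under the heading on the estimated number of subjects, gives two recruitment figures. For the biomarker phase: "We expect to identify up to 60 patients eligible for the phase 1 biomarker study". For the randomised trial: "we plan to enroll 22 patients in the double-blind treatment study (phase 2". The timing follows: "Based on our previous retrospective studies, we anticipate that we can achieve this enrollment in 12-18 months". No rate, eligible share or consent share is attached to it.

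The one retrospective count is in Section 2.a, where it supports the argument that the disease is less rare than once thought: "At UT Southwestern Medical Center, for example, we retrospectively identified 64" cases over 2010-2015. The same sentence qualifies it: "this is certainly an underestimation since awareness and clinical laboratory diagnostic tests have improved significantly in the past 4 years".

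Table 3 narrows the Phase 2 population to adults who have recently completed IV steroids and plasma exchange, with no intravenous immunoglobulin or other immunosuppression in the past year, and with a specified antibody: "Presence of one (or more) of the following autoantibodies in serum or CSF". The list names four. Phase 2 visits take place at the one centre, but subjects need not have taken part in Phase 1.

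**The concern.** The forecast is said to come from retrospective work, and the only such figure the reader can see does not produce it. About 10.7 cases a year yields 11 cases in 12 months and 16 in 18, against a target of 22. Those are identified cases before the antibody, prior-treatment and consent requirements of Table 3. Section 2.a itself notes that some treatable patients have no recognised antibody and that some forms mainly affect children, so a yield of 100% is implausible.

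Power would be at stake. N = 22 sits almost exactly at 80% for the assumed effect, with nothing to spare. If recruitment were closed at month 18 with about 16 subjects, the trial could be reported as an 80%-power study when it was not.

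**Working it through.** **Inputs.** 64 cases in 6 years (Section 2.a); 22 Phase 2 subjects, a 12-18 month window, and 20% versus 80% failure, that is W = 0.6, by a 1-df chi-square at alpha 0.05 (Section 4.a).

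**1. The plan's power figures.** Noncentral chi-square, 1 df, critical value 3.841, noncentrality N × W²:

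| W | 22 × W² | Power | Stated |
|---|---|---|---|
| 0.60 | 7.92 | 80.4% | 80% |
| 0.55 | 6.655 | 73.2% | 73% |
| 0.50 | 5.50 | 65.0% | 65% |

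All three reproduce.

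**2. Accrual at the historical rate, every case enrolled.**
- Rate: 64/6 = 10.67 a year (exact Poisson 95% interval 8.2 to 13.6).
- 12 months: 10.7 cases. 18 months: 10.67 × 1.5 = 16.0. At the upper limit: 13.6 and 20.4.
- Time to 22: 22/10.67 × 12 = 24.75 months; at the upper limit, 22/13.62 × 12 = 19.4 months.
- Rate needed: 22/1.5 = 14.7 to 22/1 = 22 a year, which is 1.38 to 2.06 times 10.67.

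The visible count therefore does not give 22 in either window.

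**3. Allowing for yield.** The documents give no eligible-and-consenting share. Assumed values of 75%, 50% and 25% give 33, 49.5 and 99 months at the historical rate. At 50%, the caseload would have to be 2.75 to 4.1 times its 2010-2015 average to meet the window. This range only illustrates the point; the antibody status and age of the 64 are not reported.

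**4. What an early stop would cost.** The plan does not call for one, but for 16 subjects (8 per arm) at 20% versus 80%:
- The plan's approximation: 16 × 0.36 = 5.76, power 67.0%.
- Exact enumeration of the two binomials: 79.8% for the uncorrected Pearson chi-square, 59.8% for Fisher's exact test.
- The same enumeration at 11 per arm: 86.7% and 73.4%.

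The approximation is poor at these sizes, so 67% should not be read as the power at 16. Nor does 79.8% come free: with 8 per arm and a common failure rate of 50%, the uncorrected test rejects 7.7% of the time. The loss from stopping at 16 depends on the test, and with either test it arises only if enrolment stops there.

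**5. Phase 1.** Setting 60 patients against 10.67 a year gives ratios of 60/16 = 3.75 and 60/10.67 = 5.6, but the populations differ. Phase 1 takes possible disease under Table 1, a broader group than identified cases, and 60 is a ceiling. The ratios show nothing about feasibility.

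**The case for a change.** The best case for acting is that the remedy is cheap and the gap is real. The protocol appeals to retrospective evidence, the only evidence shown falls short even at full yield, and calling 64 an underestimate is qualitative. If 16 cases are expected in 18 months, the chance of seeing 22 or more is about 9%; in 12 months it is about 0.2%. A funder, or the designers of the later phase III trial, would reasonably want the current annual number of eligible seropositive adults and the assumed consent share. The protocol also does not say in so many words that enrolment runs until 22 are randomised.

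Much of this stands: the forecast is not supported by the figure given. Three things limit it. First, the count ended in 2015 and the protocol was approved in 2019. With better testing, greater awareness and prospective identification with rapid in-house screening, a rise of 1.4 times or more is neither shown nor excluded. Second, Section 4.a refers to retrospective studies in the plural and does not cite the 64, which Section 2.a offers as an example, so that the forecast rests on it is an inference. Third, treating 24.75 months as a minimum would turn an admitted underestimate into a ceiling; sampling error alone brings it down to 19.4 months at full yield.

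**Conclusion.** No change is needed. The arithmetic behind the doubt is correct: 10.7 cases a year, 16 in 18 months, and a required rise of 1.4 to 2.1 times at full yield, more with any eligibility or consent loss. But a forecast above a rate that its authors describe as too low is optimistic and undocumented; it does not contradict that rate.

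The design rests on 22 patients, and the dates are only anticipated. No section closes recruitment by calendar, so a missed forecast delays the trial and leaves the sample size, the significance level, the 80/73/65% power figures and the analysis as they are. Adding a current case rate and consent share would make the feasibility case easier to follow but would alter no result. If enrolment did stop short, the report would show the number randomised, and the estimate and its uncertainty would follow from that number. The conclusion assumes that the stated plan to enrol 22 governs when recruitment ends, which is the natural reading of Section 4.a.

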Despite the burden of this potentially treatable condition, there have been no controlled prospective treatment trials for AE. Current treatments for the disease are based on expert opinion, retrospective case series, or open label immunotherapy. Most of the therapies utilized in AE are off label uses of therapies approved for other disorders, including corticosteroids, intravenous immunoglobulin, plasma exchange, “traditional” immunosuppression (e.g. cyclophosphamide), cytokine inhibition (e.g. tocilizumab) or B cell depletion (e.g. rituximab). There is particular interest in anti-CD20 therapy because of the demonstrated role of B cells in the pathogenesis of antibody-mediated disorders and the success of anti-CD20 therapy (ocrelizumab) in the treatment of multiple sclerosis, another autoimmune disorder of the brain. Additionally, unpublished data from [name] (one of the co-investigators on this proposal) shows that the characteristics of CSF lymphocytes may be predictive of response to therapy. Specifically, those patients with a large population of autoreactive plasmablasts anecdotally seem to have a better outcome than those with a large population of mature plasma cells or autoreactive memory B-cells. Targeting plasmablasts and other CD20-positive B cells acutely should be effective therapy for these disorders and prevent progression.

There is an urgent need to carry out systematic controlled studies to evaluate the efficacy of immunotherapy in AE. Retrospective data suggests that a significant number of patients will relapse without ongoing immunotherapy.³ However, immunotherapeutic drugs carry serious potential risks, so evidence of clinical efficacy is critical in order to offer such treatment to patients. We propose to conduct a prospective double-blind placebo-controlled pilot study to evaluate the efficacy of ocrelizumab in AE. These results can then be used to design a larger multi-center phase III study for the use of this drug in AE patients. This proposed pilot study will also allow the development and evaluation of biomarkers for AE which could ultimately be used to guide selection of therapy and monitor disease activity.

Form A

IRB #	STU 2018-0185
26776	

3. Study Design.

Describe the study design (e.g., single/double blind, parallel, crossover, etc.) Consider inserting a scheme to visually present the study design.

These study is comprised of two phases.

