Test of Premorbid Functioning (TOPF)	Estimate for premorbid intellectual ability
Montreal Cognitive Assessment (MOCA)	Commonly used multimodality bedside cognitive test

Form A

IRB #	STU 2018-0185
26776	

The TFLS is a validated instrumented functional test administered by a trained assessor. The score reflects ability to perform activities of daily living and higher level tasks. The 50 point raw score is converted to a T score (0 – 100) based on normative data. A change in T score of 5 points corresponds to a change of 0.5 standard deviations in the TFLS and is considered a significant meaningful change. The IADL is a simple 8 point self-administered questionnaire; a change of one point is considered significant.

After baseline procedures, subjects will be randomized to receive either intravenous ocrelizumab or matched placebo in a 1:1 ratio. Investigators, patients and treating physicians will be blinded to the treatment assignment. Patients will receive an initial dose of 300mg study medication followed by a second dose of 300mg 2 weeks later. Study medications will be handled and allocated by the research pharmacy, and infusions given in either the inpatient or outpatient clinical trials infusion center at UT Southwestern. At 6 months, patients who remain in the study will receive an additional dose of study medication (ocrelizumab 600mg or matched placebo).

Subjects will be monitored closely throughout the study with clinical assessments at months 1, 2, 3, 6, 9, and 12 as well as telephone assessments every 2 weeks between clinical visits.

Outcome assessment

The primary outcome of the treatment trial will be the proportion of patients who fail to complete the 12 month study without clinical worsening. Secondary outcomes will be time to treatment failure and change in TFLS scores at 6 and 12 months compared to baseline. We anticipate that patients treated with ocrelizumab will be much less likely to show clinical worsening compared to placebo.

Table 5: Definition of clinical worsening (treatment failure)

1. Clinician or patient/caregiver perception of clinical decline2. Worsening of patient/family reported IADL (by one point or more)3. One of the following additional features:
- Significant worsening of Texas Functional Living Scale (by ≥ 5 T points, 0.5 st deviation)- Other clinical worsening leading to hospitalization

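### Does the plain chi-square test with 11 patients per arm break its stated 0.05 enough to need replacing?

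*Combined protocol and SAP*

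**What the plan says.** Under Outcome assessment in Section 4.a, the primary outcome is binary: "The primary outcome of the treatment trial will be the proportion of patients who fail to complete the 12 month study without clinical worsening". Allocation is equal: "subjects will be randomized to receive either intravenous ocrelizumab or matched placebo in a 1:1 ratio". With 22 patients this means 11 per arm.

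The test appears only in the sample size text of Section 4.a (Estimated number of subject), where power is calculated "using a 1 degree of freedom Chi-Square Test with a significance level (alpha) of 0.05". That text assumes 15-20% failures on ocrelizumab and "an 75-80% relapse rate in the placebo group". It states 80% power at W=0.6 (20% vs 80%), 73% at W=0.55 and 65% at W=0.5.

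It then says the result would be significant (p=0.03) "even for an effect size of 46" per cent, for example "3 treatment failures out of 11 in the ocrelizumab group and 8 treatment failures in placebo group". It mentions no continuity correction and no exact test. Section 2.b (Current practice) describes the trial as a pilot and says of it: "These results can then be used to design a larger multi-center phase III study".

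**The concern.** The chi-square p-value is a large-sample approximation, and 22 patients is a small sample. A careful reader would ask whether the test really keeps to 5%, and would find that in the worst case it does not. The protocol's own example of a positive result also lies on the boundary: some tests put it below 0.05 and others above. No separate analysis section confirms the choice of test. A result like the example could therefore be called positive by one analyst and negative by another. At stake is whether a borderline pilot result, which may feed into a phase III design, carries the error rate that the protocol states.

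**Working it through.** **Inputs.** From Section 4.a: N=22, 1:1 allocation, 1-df chi-square at 0.05, failure rates of 20% vs 80% and nearby values, and the example table 3/11 vs 8/11.

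**1. The protocol's figures reproduce.**
- Power from the noncentral chi-square with 1 df and noncentrality N×W²: 22×0.6² = 7.92 gives 80.4%; 22×0.55² = 6.655 gives 73.2%; 22×0.5² = 5.5 gives 65.0%. The protocol states 80%, 73% and 65%.
- Example: chi-square = 22×(3×3 − 8×8)²/11⁴ = 22×3025/14641 = 4.545, p = 0.033. The protocol states 0.03. With the Yates correction p would be 0.088, so the uncorrected test is clearly the one meant.
- The total is 11 failures among 22, so every expected count is 11×11/22 = 5.5. The usual rule of thumb (at least 5) is met.

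**2. True error rate at 11 per arm.** List all 12×12 outcomes of two Binomial(11, p) counts, add the probabilities of those with chi-square p ≤ 0.05, and vary the common failure rate p.

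| Common failure rate | Error rate |
|---|---|
| 0.20 | 3.45% |
| 0.30 | 4.27% |
| 0.40 | 4.94% |
| 0.50 (maximum) | 5.28% |
| 0.75 | 3.94% |
| 0.80 | 3.45% |

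The rate is above 5% only between 0.411 and 0.589. The largest excess is 5.28 − 5.00 = 0.28 points. Counting only false positives that favour ocrelizumab, the maximum is 5.28/2 = 2.64%, against 2.5%.

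**3. Unequal arms (an assumption; the protocol states only 1:1).**

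| Arms | Maximum | At 0.75 | At 0.80 |
|---|---|---|---|
| 10/12 | 6.16% | 6.14% | 5.84% |
| 9/13 | 6.58% | 6.07% | 5.12% |
| 10/11 | 6.35% | 6.22% | 5.84% |
| 10/10 | 4.22% | 3.48% | 2.99% |

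**4. The example under other tests.**
- Below 0.05: Pearson 0.033, CSM (an alternative exact unconditional ordering) 0.035, N−1 chi-square 0.037, mid-p 0.048.
- Above 0.05: Boschloo 0.052, score-based Barnard 0.053, Fisher 0.086, Yates 0.088.

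**5. What a replacement would cost at 11 per arm.**

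| Test | Maximum error | Power 20% vs 80% | Power 20% vs 75% | Power 25% vs 75% |
|---|---|---|---|---|
| Chi-square | 5.28% | 86.7% | 79.2% | 70.0% |
| Barnard | 4.15% | 81.8% | 73.5% | 63.3% |
| Boschloo | 3.97% | 81.8% | 73.4% | 63.3% |
| CSM | 3.61% | 80.2% | 71.2% | 61.1% |
| Fisher | 1.73% | 73.4% | 63.0% | 51.9% |

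At 11/11 Barnard rejects the same tables as the chi-square except 3 vs 8 and its mirror. The cost at 20% vs 80% is 86.7 − 81.8 = 4.9 points of power.

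**The case for a change.** The strongest case for a change has three parts.

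First, the excess comes from the protocol's own example: removing 3 vs 8 and its mirror takes the maximum error rate from 5.28% to 4.15%. This is true, but it describes a boundary table. Any test with a 5% cut-off has such tables, and a borderline 2×2 table often changes status when many tests are tried. CSM also holds 5% and keeps 3 vs 8 positive (0.035); it gives up 2 vs 7 and 4 vs 9 instead. The verdict on the example therefore depends on which valid exact test is preferred.

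Second, no blocking is described, so a 10/12 split could occur, and the error rate then exceeds 5% even at 75-80%. This is the best part of the case, and it stands as a conditional point. The 10/11 case is weaker. It assumes that a lost patient leaves the denominator, whereas the primary outcome can be read as counting non-completers as failures.

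Third, Barnard's test roughly delivers the stated power (81.8%, 73.5% and 63.3% against 80%, 73% and 65%), so the change looks almost free. Compared with the test actually planned, it is not: it loses about 5 points at 20% vs 80%, and with arms of 10/11 Barnard's power there is 78.8%. Nor would a new example necessarily settle the matter. The table 2/11 vs 7/11 is significant by Barnard (0.041) but not by Fisher (0.080). The table 2/11 vs 8/11 is significant by both (0.017 and 0.030), but it would only replace an example that is already right for the test named.

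**Conclusion.** No change is needed. One test is named, its p=0.03 shows which version is meant, and the example and all three power figures reproduce. With 11 per arm the worst-case excess is 0.28 points, confined to common failure rates of about 0.41-0.59. If ocrelizumab had no effect and both arms failed at the assumed placebo rate of 75-80%, the test would be conservative (3.9-3.5%). The stated powers are below the chi-square's exact power, so nothing is overpromised.

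Reasonable statisticians differ over chi-square, N−1, mid-p, Barnard, Boschloo, CSM and Fisher for small 2×2 tables. Giving up about 5 points of power for a worst-case gain of this size is a matter of preference in an exploratory pilot.

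This conclusion rests on arms of 11 and 11, or close to it in effect. If the arms ended at 10/12, 9/13 or 10/11, the maximum would be about 6.2-6.6%, and an exact unconditional p-value reported beside the chi-square would be a sensible supplement. That can be left to the analyst.

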For phase 2, all visits and drug administrations will occur in the Clinical Research Units at UT Southwestern Medical Center.

Schedule of Phase 2 Study Procedures/Assessments

Study Week (Study Month)	Screening/Baseline	0	2	4 (1)	6	8 (2)	10	12 (3)	16 (4)	20 (5)	24 (6)
infusion #		1 300mg	2 300mg								3 600mg
Informed Consent	X										
Inclusion/Exclusion Criteria	X										
Medical History	X										
Pregnancy Test (females only)	X										
Telephone Contact					X		X		X	X	
Vital signs, physician exam	X	X	X	X		X		X			X
Concomitant Medications			X	X	X	X	X	X	X	X	X
Adverse Events			X	X	X	X	X	X	X	X	X
Safety Labs (CBC/CD19)	X			X		X		X			X
Safety Labs (Quantiferon, Hepatitis & JCV Serology)	X										
Serum AE Ab	X			X				X			X
Serum/CSF for B cell testing (Biorepository)	X										
Subject/Caregiver Impression				X	X	X	X	X	X	X	X
Seizure Frequency Report	X			X	X	X	X	X	X	X	X
Clinician Global Impression	X			X	X		X		X		X
Testing ⁴ - TFLS	X			X				X			X

Form A

IRB #	STU 2018-0185
26776	

Testing ⁴ - IADL	X		X	X	X ³	X	X ³	X	X ³	X ³	X	X ³	X
Testing ⁴ - SDMT	X			X				X				X	
Testing ⁴ - TMT	X			X				X				X	
Testing ⁴ - FAS	X			X				X				X	
Testing ⁴ - HVLT-R	X			X				X				X	
Testing ⁴ - TOPF	X												
Testing ⁴ - MOCA	X			X				X				X	
Study Drug Administration (placebo/ocrelizumab)		X	X									X	

¹If subject terminates study early (reaches progression endpoint)

²Telephone contact/assessments will take place every 2 weeks between scheduled clinic visit

³The IADL questionnaire will be completed at telephone contact if the patient/caregiver impression suggests clinical worsening

⁴TFLS: Texas Functional Living Scale; IADL: Lawton & Brody Instrumental Activities of Daily Living Rating Scale; SDMT: Symbol-digit Modalities Test; TMT: Trail Making Test Parts A & B; FAS: Controlled Oral Word Association Test; HVLT-R: Hopkins Verbal Learning Test-Revised; TOPF: Test of Premorbid Functioning; MOCA: Montreal Cognitive Assessment

4.b. List of the study intervention(s) being tested or evaluated under this protocol

	N/A - this study does not test or evaluate an intervention. Skip to item 4.d.		
#	Study intervention(s) being tested or evaluated under the protocol Add or delete rows as needed	Affiliate	Local Standard Practice? Indicate whether the intervention is considered acceptable practice locally for applicable institutions

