Laboratory monitoring (blood work for blood counts, CD19, and autoantibody testing) will be done at study visits. Since the subject, principal investigator and study personnel must remain blinded to treatment assignment, the laboratory results will be reviewed by an independent safety monitor (physician) who has no contact with the research subjects.

In addition, throughout the study, participants will be regularly contacted (either during clinical visits, or during telephone visits) and specifically asked about adverse events.

b. Where appropriate, discuss provisions for ensuring necessary medical or professional intervention in the event of adverse events, or unanticipated problems involving subjects.

The sponsor (Genetech) will be independently review all AE & SAE for this study. They provided a safety data exchange agreement Will the safeguards be different/between/among groups?

Yes

No

If yes, describe here

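### The only scheduled pregnancy test is at screening, at least 24 weeks before the 600 mg infusion at week 24, and no available text requires a retest

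*Combined protocol and SAP*

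**What the plan says.** All references are to the combined protocol and SAP.

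- **Entry.** Section 4.a, Table 3, lists pregnancy as exclusion 4 of the treatment trial.
- **Testing.** In the Schedule of Phase 2 Study Procedures/Assessments, the row "Pregnancy Test (females only" has one mark, at Screening/Baseline.
- **Dosing.** Section 4.a: "Patients will receive an initial dose of 300mg study medication followed by a second dose of 300mg 2 weeks later". Later, "At 6 months, patients who remain in the study will receive an additional dose of study medication"; in the ocrelizumab arm this dose is 600 mg. The schedule places it at week 24.
- **On-study laboratory work.** Section 5.a: "Laboratory monitoring (blood work for blood counts, CD19, and autoantibody testing) will be done at study visits". Because the trial is blinded, "the laboratory results will be reviewed by an independent safety monitor (physician) who has no contact with the research subjects".
- **Open-label dose.** Under Outcome assessment in section 4.a, subjects who fail treatment in the first 6 months may be offered a single 600 mg dose of ocrelizumab at the investigators' discretion. No pregnancy test is mentioned there.

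**The concern.** The protocol treats pregnancy as a reason not to start the drug and tests for it at entry. Unlike most entry conditions, pregnancy can newly arise during the months between the second and third infusions. A woman who conceived after screening, and who does not know it or does not say so, could be given 600 mg of a drug that the protocol withholds from pregnant women at entry.

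Without a test, detection depends largely on what the patient or caregiver reports. That is a weaker safeguard here than in most trials, because the disease is "characterized by seizures, cognitive impairment, movement disorders and behavioral changes".

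This is a gap in safety monitoring, not an inconsistency. The exclusion and the screening test agree with each other. The hepatitis and Quantiferon tests that support exclusion 5 are also done once.

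**Working it through.** The plan gives no figure to reproduce on this point. The check compares parts of the document and then makes a rough estimate of size.

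**1. Is the blank week-24 cell real?** The first page of the schedule has 11 columns, from Screening/Baseline to week 24. The infusion row has 11 cells, with the 600 mg dose in the eleventh. The pregnancy-test row also has 11 cells, with its only mark in the first. Both rows therefore line up with the header. Rows on the second page have 13 cells, but the pregnancy row is not among them. The columns missing from the header come after week 24 or concern early termination, so they could not hold a test before infusion 3.

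**2. Does other text close the gap?**
- The repeated safety-laboratory row covers CBC and CD19 (screening and weeks 4, 8, 12 and 24). Section 5.a adds autoantibodies. Neither names a pregnancy test.
- Table 3 contains no contraception criterion.
- Section 4.d lists a history and physical exam and an adverse-event questionnaire under Drug Administration.
- No available text says to withhold study drug if pregnancy occurs.

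**3. Length of the gap.** Screening is at or before week 0 and infusion 3 is at week 24, so the gap from test to dose is at least 24 − 0 = 24 weeks. The gap between infusions 2 and 3 is 24 − 2 = 22 weeks.

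**4. Expected number of events.** The documents give neither the number of women able to conceive nor a pregnancy rate. The assumptions are:
- 5 to 10 women able to conceive among the 22 subjects;
- 2 to 8% pregnancies per year;
- half of the women on ocrelizumab (1:1 randomisation);
- 80 to 100% still in the study at week 24, where the lower bound borrows the planning relapse rate of 15 to 20% on ocrelizumab;
- 4 to 8 weeks before a pregnancy is recognised.

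Pregnancies starting before the week-24 ocrelizumab dose = women × annual rate × 24/52 × 1/2 × proportion retained:
- low: 5 × 0.02 × 24/52 × 0.5 × 0.8 = 0.018
- high: 10 × 0.08 × 24/52 × 0.5 × 1.0 = 0.185

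Unrecognised at that dose = women × annual rate × window/52 × 1/2 × proportion retained:
- low: 5 × 0.02 × 4/52 × 0.5 × 0.8 = 0.003
- high: 10 × 0.08 × 8/52 × 0.5 × 1.0 = 0.062

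These figures leave out women first assigned to placebo who receive the open-label dose.

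**The case against.** **A rule may exist elsewhere.** Consent pages were removed, the text of section 5.b breaks off, and the product labeling is not among the documents. A contraception or retest rule could be in any of these. This stands as a limit on certainty. Even so, the schedule is what site staff work from, and it should show the test.

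**The schedule is not wholly reliable.** The Clinician Global Impression row also has 11 cells, yet it is marked at weeks 6, 10 and 16, which are telephone contacts, and is blank at the week 8 and 12 clinic visits. A matching cell count therefore does not prove that every mark is right. That is fair, but it gives no sign that a week-24 pregnancy mark was lost.

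**Section 4.d is weak evidence of absence.** It does not name the pregnancy test even under eligibility, where one is certainly done, so the test may sit under the general label for ocrelizumab safety labs. That label recurs under clinic visits. Section 4.d therefore adds little either way. The schedule, however, gives the pregnancy test its own row, apart from both safety-lab rows, and section 5.a describes the repeated tests without it.

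**Other safeguards exist.** Week 24 has a physician exam, concomitant-medication and adverse-event checks, and subjects are telephoned every two weeks between visits. These would probably catch a known pregnancy. They would not reliably catch one that nobody suspects. The documents do not say how impaired participants will be at month 6.

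**The size is assumed and small, and the remedy is partial.** Both points stand. The larger range (0.02 to 0.18) includes pregnancies that would already have been recognised. A week-24 test also does nothing for conceptions soon after the first two infusions or after the third.

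**Conclusion.** The concern holds. On the available text, the last scheduled dose is given at least 24 weeks after the only pregnancy test, and there is no retest or withholding rule. Under the stated assumptions, 0.003 to 0.06 unrecognised pregnancies would be exposed at that dose in the whole trial. The case for the change therefore rests on a serious, avoidable exposure set against a very low cost, not on a high expected count. No statistical figure in the plan and no part of the primary analysis is affected.

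The same gap may apply to the discretionary open-label dose. That is less certain, because the early-termination column is missing from the schedule as extracted. Confidence overall is medium, because a rule could lie in text that is not available.

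**What to change.** - Mark the existing pregnancy-test row at week 24, using urine or serum from the blood already drawn at that visit, with the result known before infusion.
- Require a negative test before any open-label dose.
- State that study drug is withheld if the test is positive and that follow-up continues.
- State that this result goes to the infusing staff before the drug is given. Under section 5.a, laboratory results otherwise go to a monitor who has no contact with subjects. A pregnancy result does not reveal the treatment arm, so blinding is not at risk.

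A retest at week 2 would add little and is not proposed.

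**Cost.** The change is one mark in the schedule and a short statement on withholding and reporting. A subject either reaches the week-24 dose or is an early failure who may be offered open-label drug. That means at most one extra test per woman, and at most 1 × 22 = 22 in all. The downside is a short wait before infusion and, rarely, an omitted dose.
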